Blood Transfusion: Early studies (1976, 1980) in healthy volunteers failed to show an improvement in VO_2 max after transfusing liquid RBCs, possibly due to the low quality of the stored RBCs.^{46,47} In contrast, later studies that transfused at least 2 units of cryopreserved, deglycerolized autologous RBCs to healthy volunteers showed consistent increases in VO_2 max, even if pre-transfusion Hb was as high as 16 g/dL.^{44,45,48-50} In other words, the increase in VO_2 max does not require anemia at baseline to show improvements in VO_2 max. For example, in 8 volunteers, Celsing et al removed 450 mL of whole blood 5 times, resulting in lower VO_2 max at A (anemia; figure right).⁴⁸ One unit of cryopreserved RBCs was transfused on visits 1, 2, 3, and 4 over several weeks, resulting in a stepwise increase in both hemoglobin and VO_2 max (L/min). As expected, control subjects (n=8, dotted line) showed no change in hemoglobin or VO_2 max.

Our preliminary data are consistent with the above studies, since we showed a predictable increase in VO_2 max after transfusion with 2 units of 7-day RBCs. None of these previous studies, however, determined whether storage duration impairs the ability of the RBCs to deliver oxygen, which was the focus of our pilot study and will be characterized further in the proposed study.

D. RESEARCH DESIGN AND METHODS

[figure not shown]
This is a single-center, randomized, partially blinded study.

1) Overview

After consent and screening the study interventions last 6 weeks and consist of 2 phlebotomy visits at Stony Brook hospital and transfusion with 2 units of autologous AS-3 RBCs that are either 7-, 28-, or 42-days old. Subjects will be randomized (1:1:1) to either cycle A (7 day RBCs), cycle B (28 day RBCs, or cycle C (42 day RBCs).

During week 6 of each cycle, subjects will have 3 study visits consistent with the pilot study we just completed.

- On Monday subjects will have a VO_2 max test.
- On Wednesday, they will be transfused with 2 units of autologous RBCs (each over 1 hour), followed by a VO_2 max test 2 hours later to assess the “acute” effects of transfusion (intravascular volume + RBC mass), which is a secondary endpoint of the proposed study.
- On Friday, they will have a VO_2 max test, which is compared with the baseline VO_2 max result (Monday) in order to calculate a delta VO_2 max related to transfusion (primary endpoint), avoiding potential confounding from acute intravascular volume effects.

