Removal of waste unit(s): During each cycle, subjects will also have a second visit to Stony Brook. For example, Cycle A has 2 units removed at Week 0, Cycle C has 2 units removed at Week 5. These units are removed for 2 reasons: 1) to maintain blinding for the 7- vs 42-day RBC comparison since subjects will not know whether they are receiving their 7- or 42- day RBCs; and 2) to induce mild anemia (projected Hb 11-12 g/dL), which, while still extremely safe, may enhance increases in VO_2 max from transfusion in order to detect more robust differences between study arms. We have numerous safeguards in place to protect human subjects (see Human Subjects section).

Blinding: We cannot fully blind Cycle B (28-day RBCs). However, we plan to partially blind the subject by informing them that they may receive either 2 units of 28-day RBCs or 1 unit of 28-day RBCs and 1 unit of 7-day RBCs. This “deception” should be allowed since it is inconsequential to the subjects, as they will already have agreed to receive 7- and 42-day RBCs in other cycles, and is merely done to improve blinding of the study. Notwithstanding the above, we believe this strategy is a reasonable compromise since VO_2 max is a quantitative measurement and subjects are motivated fit athletes who, in our experience, exercise to exhaustion.²⁵⁻³⁵ Furthermore, subjects are not likely to have preconceived ideas/bias about the efficacy of

28-day RBCs. In cycles A and C, 2 units of blood will be removed 7 days before the transfusion week. However, for cycle B, only 1 unit of blood will be removed 7 days before the transfusion week because their initial 2 unit phlebotomy will be at day 28 and not at day zero. They will have had 14 fewer days to recover hemoglobin compared to cycles A and C. Based on our estimates of RBC mass removal and restoration (synthesis), we anticipate that this will result in a pre-transfusion Hb that is similar to cycles A (7-day) and C (42-day).

2) Research Site

All study procedures will be completed at a single center, Stony Brook University Hospital.

3) Study Sample

Consistent with our pilot data, qualified volunteers will be enrolled at Stony Brook University Hospital.

4) Screening

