- xi. Recent history of blood donation: a) Single whole blood unit donation within the past 8 weeks; b) Double RBC donation by apheresis within the past 16 weeks; or c) Plasma donation by apheresis within the past 4 weeks
- xii. Inadequate RBC mass based on TBV <4500 ml (above) or screening Hb <14.0 g/dL

Screening tests (performed after consent is obtained): The following will be performed to confirm eligibility and optimize the safety of subjects: 1) written questionnaires that provide written confirmation of eligibility for blood donation and confirm appropriateness for exercise testing (PAR Q+ questionnaire);⁵¹ 2) hemoglobin must be ≥ 14.0 g/dL; 3) hemoglobin A1c to rule out diabetes; 4) Sickledex to rule out sickle trait or anemia; 5) ECG to rule out prolonged QTc; 6) height and weight to calculate and confirm required total blood volume (above); 7) spirometry to rule out undiagnosed pulmonary disease; and 8) serum hCG test if female

Subjects will be informed that during the study they may take a multivitamin but they should not take iron supplements.

5) Procedures

Blood Donation, Processing, and Storage (Visit B on Day 0, Visit C on Day 35)

We will use the same procedures successfully used in our recently completed pilot study and our TASER study.²⁴ Stony Brook's Transfusion Services is registered and licensed by the FDA and accredited by the American Association of Blood Banks. [name], medical director of Transfusion Services, is a co-Investigator this study.

After passing a written screen at Stony Brook University Hospital's Blood Bank, 2 units of RBCs will be collected in CP2D via venous apheresis using a Trima Accel® Automated Blood Collection System: (<http://www.caridianbct.com/location/emea/products-and-services/Pages/trima-accel-collection-system.aspx>). Blood will be processed by technicians at this center using standard techniques. All RBCs will be leukoreduced (pre-storage), tested for all required infectious diseases, stored in AS-3 additive solution. AS-3 RBCs will be used since apheresis products collected by Trima Accel® have only been validated for AS-3. There are no data to suggest that our results would not be generalizable to AS-1 or AS-5 RBCs. Before every blood donation, each subject's hemoglobin will be measured, and only those with a value ≥ 12.5 g/dL will be allowed to donate.

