VO_2 max testing will be performed in Level 2 of the Health Sciences Center. Each subject will be instrumented with a 3-lead ECG to monitor cardiac rhythms and a pulse oximeter to record heart rate. Mixed expired oxygen, carbon dioxide, breathing frequency, tidal volume, minute ventilation, oxygen consumption, and carbon dioxide production will be measured with a metabolic cart. Data will be recorded every 30 seconds as 30-second averages. Subjects will breathe air through a two-way non-rebreathing valve connected to the metabolic cart.

Subjects will be seated on a cycle ergometer. The seat height will be adjusted so that when sitting squarely on the seat with the pedal in the lowest position, a slight bend of approximately 10 degrees will be maintained at the knee. Digital displays of rpm will be visible to the subjects.

Three minutes of initial resting baseline measures will be collected before the start of exercise. The subject will then begin to pedal the cycle ergometer at a cadence of 75 rpm. Resistance will be manually set according to the progressive protocol shown in the Table (right).

Stage	Time (min)	RPM (rpm)	Total Workload (watts)	Leg Load (kp)
1	0 - 3	75	50	0.68
2	3 - 6	75	100	1.36
3	6 - 9	75	150	2.04
4	9 - 10	75	175	2.38
5	10 - 11	75	200	2.72
6	11 - 12	75	225	3.06
7	12 - 13	75	250	3.4
8	13 - 14	75	275	3.74
9	14 - 15	75	300	4.08
10	15 - 16	75	325	4.42
11	16 - 17	75	350	4.76
12	17 - 18	75	375	5.1
13	18 - 19	75	400	5.44
14	19 - 20	75	425	5.78
15	20 - 21	75	450	6.12

A rating of perceived exertion (RPE) will be obtained at the end of each exercise stage. The VO_2 max test will be terminated when the subject reaches volitional fatigue, or, in the very unlikely event, achieves one of the other test termination criteria as defined (see table in Human Subjects: Adequacy of Protection Against Risk).

The screening VO_2 max test (Visit A) will allow each subject to become familiar with this testing protocol.

VO_2 max is determined as the highest oxygen consumption averaged over 2 30-second periods, which typically occurs in the last stage of the progressive maximal exercise test. Peak heart rate is considered to be heart rate at VO_2 max. Maximum heart rate (HR_{max}) is considered to be heart rate at or near VO_2 max.

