 - c. The subject may experience pain around the IV site or in the arm with the IV. Investigators will select the largest available vein in the forearm or antecubital fossa to minimize pain during blood infusion.
 - d. Mistransfusion, arising from errors in unit labeling, component preparation or other clerical errors occurs in 1:16,000 - 1:25,000 autologous donations. To minimize the risk of mistransfusion, which in the worst possible case may trigger a fatal or serious acute reaction, multiple safeguards to prevent this are written into our study protocol and include the following:
 - i. multiple sample and bag identification checks
 - ii. 2 persons will confirm the subject's identity with the stored RBCs, using established hospital approved standard Stony Brook Hospital transfusion procedures
 - iii. a standard crossmatch will be performed between the subject's stored donated unit and a fresh sample of the subject's blood (if an antibody is found, an extended crossmatch will be performed)
 - iv. only one subject will be transfused on a given day to minimize risks

- v. the research subject will be asked to review their signature on the labels for their autologous units to confirm they are receiving their own blood
4. Risks associated with exercise (VO₂ max) testing: The most common complaint from those performing the exercise test on a bicycle is thigh pain during the test. In healthy volunteers, the likelihood of death or a serious complication, e.g. sustained arrhythmia, is low, but not impossible. The following is language from a recent publication:
Risks of Physical Activity, Exercise Training, and Exercise Testing
*Recommendation 1: Maximal exercise stress testing is associated with a very low risk of fatal and non-fatal cardiac events in either healthy asymptomatic or clinical populations. In healthy, asymptomatic individuals, the respective incidences of fatal and nonfatal events are approximately 0.3-0.8/10,000 tests and 1.4/10,000 tests (Level 3, Grade B).*⁵¹
 5. Risks associated with loss of protected health information: As with any participation in a research study there is a small chance that a loss of confidentiality could occur, but our use of standard risk management procedures will minimize this risk.

Adequacy of Protection Against Risks

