 - b. If the blood is stored longer than 14 days prior to transfusion, a sample of the stored blood will be tested for the presence of bacteria 7 days before re-infusion. If tests are positive for the presence of bacteria, the subject will be notified and their participation in the study will not continue.
 - c. During blood transfusion (which will occur in a Health Sciences Center lab or the SBUH Blood Bank), subjects will be monitored by an experienced RN study coordinator and one of the physician investigators will be either at the bedside or immediately available. We will monitor temperature, blood pressure, ECG, and pulse oximetry in order to detect possible transfusion reactions. In addition, consistent with our previous pilot study, each RBC unit will be administered over 60 minutes to minimize the likelihood of transfusion associated circulatory overload (TACO) or pulmonary edema, which is unlikely in healthy, fit subjects.
 - d. Investigators will select the largest available vein in the forearm or antecubital fossa to minimize pain during blood infusion.
 - e. To minimize the risk of mistransfusion, which in the worst possible case may trigger a fatal or serious acute reaction, multiple safeguards to prevent this are written into our study protocol and include the following:
 - i. multiple sample and bag identification checks
 - ii. 2 persons will confirm the subject's identity with the stored RBCs, using standard Stony Brook Hospital transfusion procedures
 - iii. a standard crossmatch will be performed between the subject's stored donated unit and a fresh sample of the subject's blood (if an antibody is found, an extended crossmatch will be performed)
 - iv. only one subject will be transfused on a given day to minimize risks
 - v. the research subject will be asked to review their signature on the labels for their autologous units to confirm they are receiving their own blood

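### The subject's signature check on the unit labels is an unprotected route to unblinding in the 7- versus 42-day comparison

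*Combined protocol and SAP*

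**What the plan says.** **The blind.** Section D, 1) Overview, opens with "This is a single-center, randomized, partially blinded study". Under Removal of waste unit(s), the first reason given for the extra draw is "to maintain blinding for the 7- vs 42-day RBC comparison since subjects will not know whether they are receiving their 7- or 42- day RBCs". The mechanism is that subjects in both arms give blood twice and get only one donation back: "Cycle A has 2 units removed at Week 0, Cycle C has 2 units removed at Week 5". Section D, 5) Procedures, gives the timing of the two donations: "Visit B on Day 0, Visit C on Day 35".

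**The label check.** Section G lists safeguards against mistransfusion twice: under Risks to Subjects (item 3, d, v) and under Adequacy of Protection Against Risks (item 4, e, v). In both, "the research subject will be asked to review their signature on the labels for their autologous units", the purpose being to confirm that the blood is the subject's own.

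**The endpoint.** Under Detailed Description of VO₂ max, the "test will be terminated when the subject reaches volitional fatigue". The primary outcome is the proportional change from Monday to Friday of week 6, with transfusion on the Wednesday between.

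**The concern.** In cycles A and C the donation that the units come from identifies the arm: Day 0 blood is 42-day blood and Day 35 blood is 7-day blood. One section keeps that fact from the subject. Another puts in front of the subject an object that may carry it, and nothing in the protocol connects the two.

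The timing matters. The label check belongs to Wednesday's transfusion, so anything learned from it comes after Monday's baseline and before the Wednesday and Friday tests. An expectation effect would enter the Monday-to-Friday change directly, and the baseline could not absorb it. The test ends when the subject gives up, so effort can influence the result. Exercise duration, a secondary outcome, is exposed in the same way. The comparison is also one-sided: if subjects expected old blood to perform worse, the bias would run in the direction of the hypothesis.

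A positive result in 20 subjects would then be open to the criticism that expectation contributed, and this could not be repaired after the trial.

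**Working it through.** **1. The plan's sample size.** Inputs from section E, Sample Size: mean change 8.7% (7-day) and 1.6% (42-day), SD 6% in each arm, one-sided 0.05, power 80%.

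- Effect size: (8.7 − 1.6)/6 = 7.1/6 = 1.183, as stated.
- Power of the two-sample t-test: P(T > t with 2n − 2 df at 0.95), where T is noncentral t with noncentrality (δ/σ)·√(n/2).
- n = 9 per arm: power 0.775. n = 10 per arm: noncentrality 1.183 × √5 = 2.65, power 0.816.

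The stated 10 per group is reproduced, so the primary comparison has 20 subjects. The concern does not touch this figure.

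**2. The text side by side.**

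| Step | What the protocol gives | Where |
|---|---|---|
| Two donations in cycles A and C | Day 0 and Day 35 | D, 1) and 5) |
| What must stay hidden | Which donation is returned | D, 1) Removal of waste unit(s) |
| What the subject is shown | The signature on the labels of the returned units | G, both safeguard lists |
| What else the label carries | Not described | – |
| Step to hide the collection day | None stated | – |
| Stated exception to blinding | Cycle B (28-day) only | D, 1) Blinding |

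The first three rows are in the text. Whether the route leads to unblinding depends on the fourth, which the documents leave open.

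**3. What an expectation bias would do (illustration).** Suppose there is no true difference, SD is 6 and n = 10 per arm. Let unblinding shift the 7- minus 42-day difference by an average of b percentage points. The false-positive rate comes from the same formula with δ = b, that is, noncentrality (b/6)·√5 on 18 df. The values of b are assumptions; the documents give none.

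| b (points) | Share of the planned 7.1 | Noncentrality | One-sided false-positive rate |
|---|---|---|---|
| 0 | 0% | 0 | 5.0% |
| 1 | 14% | 0.37 | 9.9% |
| 2 | 28% | 0.75 | 17.7% |

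Here b is an average over the whole comparison. If half the subjects in each arm were unblinded and full unblinding would shift the difference by 2 points, the average shift is about 0.5 × 2 = 1 point, and the 9.9% row applies.

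**The case against.** The deciding fact is not in the documents. The subject is asked to review a signature, not to read a label, and a signature can be shown without the rest. When and how the label is signed is not described, and bedside identity checking follows hospital procedures that are not before us. Those may already hide dates; silence shows neither that they do nor that they do not. This stands, and it limits the point to an open route.

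Some design features also restrain effort bias. Subjects must reach at least 95% of predicted maximum heart rate at screening, one facilitator attends every test, and peak heart rate and perceived exertion are recorded. Pilot peak heart rates averaged 184 in both arms. These would help to detect or limit reduced effort, but they do not stop the subject learning the arm. Section E names hemoglobin and BMI as adjustment variables and plans no analysis of effort. The argument that the endpoint is quantitative and the subjects are motivated athletes is made in defence of cycle B; it does not address the labels.

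The direction of bias is presumed as well. No passage reports what subjects believe about 42-day blood.

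A reader might infer that unblinding would make the waste draw pointless. It would not: the protocol gives a second purpose, inducing mild anemia to enhance the VO₂ max response, and that survives.

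Finally, the check guards against a potentially fatal error, so any change must leave it intact. That is accepted.

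**Conclusion.** The concern holds as an unprotected route to unblinding. A stated step works against a stated blind, in the primary comparison, on an endpoint that depends on effort, and no passage protects against it. The label of partial blinding does not excuse the gap, because the only exception the protocol explains is cycle B.

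Two stronger readings are not supported. One is that subjects will be unblinded, up to all 20 of them. That needs identifying information on the label, visible to the subject, and noticed and understood, none of which the documents establish. The other is that the trial's false-positive rate is 10% to 18%. Those figures only show how sensitive a comparison of 10 per arm is to an average bias of 1 or 2 points from any source. The size and direction of the bias are assumptions, and the rate falls if only some subjects are unblinded.

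If the subject sees only an undated signature, this route is closed and a sentence saying so settles the point.

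**What to change.** In both section G safeguard lists (3, d, v and 4, e, v), state that information identifying the collection day is shielded from the subject's view during the signature check. That covers collection and expiry dates, donation numbers and any date beside the signature. A removable cover or an undated signature tag would do; the method can be left to the blood bank. State in the same place that the subject's signature check, the bag identification checks and the two-person check against the full label are kept unchanged. If existing procedure already shields this information, say so.

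Optionally, ask each subject after Friday's test which arm they believe they were in, so that the success of the blind can be reported.

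The cost is one extra handling step for staff, which the blood bank should fit into its own sequence of checks. Sample size, visit schedule and primary analysis do not change.
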